1.4 Research Benefit

This study will provide treatment in the form of hemodialysis three times a week during the study period to consenting and committed patients marked by signing on the explanation sheet after approval. In addition, subjects will receive routine Epoetin treatment during the study period.

CHAPTER 2. LITERATURE REVIEW

2.1 Chronic Kidney Disease (CKD)

Chronic Kidney Disease (CKD) is kidney damage due to structural or kidney function abnormalities that occurs for more than 3 months. The kidneys have various functions including excretion, endocrine and other metabolic functions. Glomerular filtration rate (GFR) is one component of excretion that is generally used as an index of renal function because in general kidney function will decline after damage to the spread structure and decrease in other kidney function decreases with glomerular filtration rate in CKD (KDIGO, 2013). The criteria for Chronic Kidney Disease (CKD) can be seen in the following table:

Table 1. CKD criteria (KDIGO, 2013)

Parameters of kidney damage (one or more)	
• Albuminuria (AER> 30 mg / 24 hours; ACR> 30 mg / g [$> 3\text{mg} / \text{mmol}$])• Urinary sediment abnormalities• Electrolyte abnormalities and others due to tubular damage• Abnormalities detected by histology• Structural damage detected by imaging• History of kidney transplants
Decreasing Glomerular Filtration Rate (LFG)	$< 60 \text{ mL/minute}/1.73 \text{ m}^2$

Based on the National Kidney Foundation Kidney Disease Improving Global Outcomes (NKF-KDIGO) in 2012, the classification of Chronic Kidney Disease (CKD) was divided based on glomerular filtration rate and albuminuria (Figure 1).

Prognosis of CKD by GFR and Albuminuria Categories: KDIGO 2012				Persistent albuminuria categories		
				Description and range		
				A1	A2	A3
				Normal to mildly increased	Moderately increased	Severely increased
				<30 mg/g <3 mg/mmol	30-300 mg/g 3-30 mg/mmol	>300 mg/g >30 mg/mmol
GFR categories (ml/min/ 1.73 m ²) Description and range	G1	Normal or high	≥90			
	G2	Mildly decreased	60-89			
	G3a	Mildly to moderately decreased	45-59			
	G3b	Moderately to severely decreased	30-44			
	G4	Severely decreased	15-29			
	G5	Kidney failure	<15			

Green: low risk (if no other markers of kidney disease, no CKD); Yellow: moderately increased risk; Orange: high risk; Red, very high risk.

Figure 1. Classification of Chronic Kidney Disease based on Glomerular Filtration Rate and albuminuria (KDIGO, 2012)

In patients with CKD, a decrease in the glomerular filtration rate causes a buildup of chemicals such as potassium and urea. Hemodialysis therapy, which is a blood cleansing process using a kidney replacement in the form of a dialyzer machine, is given to patients with CK level 5 or the final level or GFR <15 mL / minute / 1.73 m². This process involves the use of a dialysate containing sodium bicarbonate, sodium chloride, acid concentrate, and water distilled as an osmosis medium. The physiological working principle of hemodialysis is filtration, diffusion, osmosis, and ultrafiltration which are influenced by temperature, viscosity, and size of the molecule itself (Vadakedath & Kandi, 2017).

People with CKD often also suffer from anemia complications caused by a decrease in kidney function. Anemia diagnosis is given to adult PGK patients if the Hb concentration is <13 g / dl in men or <12 g / dl in women. This condition can occur when a decrease in kidney function is up to 50%. Iron therapy can be performed on CKD patients with anemia who have low iron levels, which is known by conducting laboratory tests for ferritin <200 ng / L and transferrin saturation <30%. In addition, CKD patients with anemia can be given Epoetin therapy to increase levels of red blood cells or erythrocytes in the blood (Pollock et al. 2008).

Giving Epoetin in patients with CKD who undergo hemodialysis begins after symptoms of uremia, excess fluid, and stable hypertension. In addition, administration of Epoetin can only be done after all causes of anemia except erythropoietin deficiency are overcome, especially iron deficiency, folic acid, vitamin B12, and the presence of bleeding (Pollock et al. 2008).

2.2 Biosimilar

Biological products contain active compounds derived from living cells or organisms and are very necessary for the treatment of various serious and chronic conditions. Most biological products used clinically are groups of proteins with varying sizes and complexity. The production process of biological products is more complicated than medicinal products produced through a synthesis process with chemical reactions, because it often involves the engineering process of DNA recombination.

In the production process, the biological products produced can vary between batches which can affect the safety and efficacy of the product as a whole. Determination of standard variations is needed to ensure that active compounds can work in accordance with the objectives and at the intended level. Strict control of the quality of biological products is applied to each batch of production, both from physicochemical properties, biological activities, activity, purity, degree of sterilization, and stabilization.

Biosimilar products are products that are similar to other biological products whose period of protection has ended. Biosimilar products must have similarities and sequences of amino acids or proteins and protein folding structures that determine their biological activity. In addition, biosimilar products are also not allowed to have different posology and administrative routes unless they have an effect on product safety and efficacy. Based on the level of similarity with the originator, biosimilar products are divided into 4 levels (Figure 2) (EMA, 2017).

Highly similar to the reference medicine	The biosimilar has physical, chemical and biological properties highly similar to the reference medicine's. There may be minor differences from the reference medicine which are not clinically meaningful in terms of safety or efficacy.
No clinically meaningful differences compared with the reference medicine	No differences are expected in clinical performance. Clinical studies that support the approval of a biosimilar confirm that any differences will not have an effect on safety and efficacy.
Variability of biosimilar kept within strict limits	Minor variability is only allowed when scientific evidence shows that it does not affect the safety and efficacy of the biosimilar. The range of variability allowed for a biosimilar is the same as that allowed between batches of the reference medicine. This is achieved with a robust manufacturing process to ensure that all batches of the medicine are of proven quality.
Same strict standards of quality, safety and efficacy	Biosimilars are approved according to the same strict standards of quality, safety and efficacy that apply to any other medicine.

Figure 2. Similarity level of biosimilar product toward the originator (EMA, 2017)

Biosimilar products are different from generic products because the production of generic products is carried out through a chemical synthesis process and does not involve variability so that the end product can have a similarity level of up to 100% (Table 2).

Table 2. Comparison of generic products with biosimilar products (EMA, 2017)

	Generic product	Biosimilar product
Production process	Chemically synthesized	Biological process
Final result	The exact same molecule	Molecules with high similarity levels
Molecule size	Small, can be easily characterized	Large, complex structures require technology for characterization
Development process	Emphasizes the bio-equivalence (speed of release of active compounds)	Emphasizing biosimilarity (structure, biological functions, efficacy, safety, and immunogenicity)

The biosimilar regulation was first compiled by the European Union in 2006 with the approval of the first biosimilar product, the somatotropin hormone. Approval of biosimilar products is given based on a balance between positive benefits and risks based on biosimilarity with the originator.

This is obtained through comparative studies to find out clinical data between biosimilar products and their originators.

Based on applicable regulations in the European Union, biosimilar producers must be able to show data as proof that the product has been produced to applicable standards and is intended for certain clinical uses. Some requirements include characteristic structure, physicochemical properties, purity, biological activity, product composition, formulation, manufacturing process, and stability of active ingredients and products during storage (EMA, 2017).

Clinical trials for biosimilar products do not need to be done for all important stages (phase 1, 2, and 3 clinical trials) to find out analytical and functional data because these two aspects have been carried out by the originator. The comparability, security, and efficacy between biosimilar products and the originator are preferred (EMA, 2017).

2.3 Erythropoietin

Erythropoietin (EPO), otherwise known as epoetin is a glycopeptide hormone (figure 3) produced by renal erythropoietin producing cells in the kidneys. This hormone is functioning as a stimulator to produce red blood cells in the human red marrow. Increased hormone production is happening when low-oxygen level detected in kidney. EPO in humans was first isolated from anemic patients in 1977. The gene that encodes EPO in humans was first isolated in 1983. After one year later, the EPO gene was successfully cloned for the first time shown in the Chinese Hamster Ovary (CHO) cell. This cloning technology then became a stepping stone in the development of recombinant human EPO (rhEPO) as an anemia drug in patients with chronic kidney disease.

[figure not shown]

Figure 3. Amino acid sequence and Erythropoietin primary structure

Erythropoietin is known to cause physiological effects if it binds to EPO receptors (EpoR). EPO binds to its receptors on the surface of stem cells which will differentiate into red blood cells. EPO is known to have a mechanism of action on cells by activating the JAK2 signal cascade. The initiation of the JAK2 pathway will also activate the signal cascade on the STAT5, PIK3, and MAPK lines. The signaling causes erythroid cell differentiation and division. In addition, the SOCS1, SOCS3 and CIS paths are also activated and play an antagonistic role as a negative regulator of EPO. EPO receptors (EpoR) are found most frequently in stem cells in the red marrow. Even so, EpoR is also found in other tissues, such as the heart, muscles, kidneys, peripheral nerve networks and central nervous networks.

The level of EPO in blood in normal humans is around 10 mU/mL. Meanwhile, in conditions of hypoxia or lack of oxygen, EPO production has increased up to 1000 times to reach 10,000 mU/mL in blood. In adults, EPO is produced mainly in cells in the kidney, but a small fraction of the fraction of EPO in the blood is also produced by the liver and pericyte cells in the brain.

Regulation of EPO production is governed by a reciprocal mechanism of oxygen and iron levels in the blood.

2.4 Epodion®

Epodion® is an alpha rhEPO product produced by PT. Daewoong Pharmaceutical Company Indonesia. This product is used in conjunction with other clinical treatments for anemic patients due to chronic kidney disease or due to chemotherapy. Yellowish transparent Epodion® injection solution which can be injected intravenously or subcutaneously. Epodion® has four products with different EPO content, including 2000 IU, 3000 IU, 4000 IU, and 10000 IU.

At the beginning of Epodion® use, patients are given a dose of 50 units/kg of body weight three times a week which can be done intravenously or subcutaneously. If needed, the dose can be increased to 75 units/kg at 4-week intervals from the initial administration. If the increase in hemoglobin level increases by more than 2 gr/dL at the initial dose, the administration of Epodion® must be reduced to 2 times a week. Repair doses can be continued until the patient's hemoglobin level becomes 10 gr/dL. Anemia that has been overcome can be continued with a maintenance

dose of between 25 to 50 units/kg, 2 or 3 times a week. The expected hemoglobin range for treatment is 10-12 gr/dL. The initial hemoglobin level determines the treatment dose. In addition, the patient's age is also important in determining the dose. The dosage for the use of Epodion® should not exceed 200 units/kg and the frequency of administration is not more than 3 times a week. During treatment, the patient's iron levels need to be controlled. Chronic kidney failure patients who do not undergo hemodialysis, a dose of 70-150 units/kg per week is proven to maintain hematocrit levels 36-38% for more than 6 months.

Research on the effects of Epodion® on human bone marrow cell culture shows that Epodion® stimulates the formation of red blood cells and does not affect the formation of white blood cells. Animal studies using Epodion® showed in vivo efficacy in test animals. In addition, no cytotoxic effects were detected, changes in behavior, locomotor activity, circulation or breathing in test animals.

The time needed to reach maximum concentration in uremia patients averages 12-28 hours with subcutaneous administration. The bioavailability of Epodion® by subcutaneous administration is 23-42% compared with intravenous administration. Half-life of Epodion® given intravenously to healthy volunteers and kidney failure patients ranges from 4-12 hours with a distribution volume reaching 1 to 2 times the plasma volume. This is similar to the results found in studies in mice with uremia and normal mice. The half-life of the terminal Epodion® by subcutaneous administration in uremia patients averages 13-28 hours, longer than intravenous administration.

The most common side effect is hypertension or worsening hypertension. This increase in blood pressure can be treated with antihypertensive agents. If the hypertension that occurs cannot be overcome with anti-hypertensive drugs, it is recommended to temporarily stop giving Epodion®. Therefore, it is recommended to monitor the possibility of a hypertensive crisis with symptoms resembling encephalopathy (eg, headache, confusion, sensorimotor disorders, tonic clonic (seizures), including in patients with normal or low blood pressure.

In addition, leukocytosis, eosinophilia can sometimes occur. Granulocytopenia can sometimes occur in premature infants. Increases in serum potassium, BUN, creatinine and gout have been reported to occur occasionally. Although rare, thrombocytosis can occur. Reported red cell hypoplasia after administration of Epodion® product in patients with chronic kidney failure from several months to several years is rare. In addition, there may be an increase in platelet counts during Epodion® therapy, especially if given IV. This increase in platelet counts associated with the dose of Epodion® given is usually within normal limits and will improve if Epodion® therapy is given. The incidence of thrombocytosis is very rare. However, it is recommended to monitor platelet levels during the first 8 weeks of Epodion® therapy.

Often, a higher dose of heparin is needed during hemodialysis due to an increase in hematocrit levels. In addition, a dialysis system blockage may occur if heparinization is not optimal. Shunt thrombosis can occur in patients who tend to be hypotensive or patients with complications of the arteriovenous fistula (eg, aneurysm, stenosis). In these patients it is recommended to give thrombosis prophylaxis to administration of acetalsalate. In some patients, there is a decrease in serum ferritin levels together with an increase in hematocrit. For this reason, it is recommended to provide 200 mg / day of oral iron (Fe²⁺) substitution in patients with serum ferritin levels <100 ug / L or transferrin saturation <20%. Then, there is a temporary increase in serum potassium and phosphate levels. Therefore, it is recommended to monitor these parameters regularly.

CHAPTER 3. STUDY DESIGN OVERVIEW

3.1 Study Design

This study is an open label, randomized, active drug-comparative, parallel-designed, multi-center study in hemodialysis patients with anemia.

3.2 Number of Research Subjects and Estimated Number of Samples

3.2.1. Number of Subjects

The total number of subjects in this study is 100 subjects. Only subject who achieve baseline target Hb level 10-12 g/dL will continue to maintenance period. Subject will be randomized into 2 study arms. For the randomized allocation code between reference product (Eprex®) and test product (Epodion®) will be maintained ratio 1:1.

Study Group	Epodion®	Eprex®
Evaluated	50 Subjects	50 Subjects

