Dosage & Administration, and Route of Administration	
Initial Epoetin dose administered according to previous dose. In Maintenance period, Epoetin dose may be increased or decreased at an appropriate level according to the condition of the subjects.
								
Number of subjects	
  
 	Study Group (Epodion®)	Control Group (Eprex®)	Total Sample Size	
   
 Evaluated Case	50	50	100	
  
		Study Group (Epodion®)	Control Group (Eprex®)	Total Sample Size	Evaluated Case	50	50	100
	Study Group (Epodion®)	Control Group (Eprex®)	Total Sample Size						
Evaluated Case	50	50	100						
	
Inclusion Criteria:
 
a. Male or female patients who are at least 18 years old and younger than 75 years of age at the time of screening visit.
								

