3.2. Rationale Number of Subject

A sample size of 90 subjects will be determined with difference 0 g/dL, standard deviation 0.8 g/dL, statistical power 90%, randomization ratio 1:1 to demonstrate equivalence at 5% significance level and equivalence margin ± 0.5 g/dL. Assumption of difference and standard deviation for sample size estimation in this study was derived from PDA10 ITT set. Difference between treatment groups in PDA10 ITT set was -0.009, but this study assumed to be 0. Standard deviation 0.8 was an approximate estimation derived from two-sided 90% confidence interval [-0.189, 0.171]. After an assumption of 10% drop-out rate for this trial, about 100 subjects will be enrolled to the trial. The sample size calculated using the POWER procedure (Proc Power procedure) of SAS ver. 9.4 (SAS Institute, Cary, NC, USA).

```

*****
+ PROGRAM NAME. : SAS Proc Power_EPO.sas
+ OUTPUT : EPO_Biosimilar_Sample Size_20191014.pdf
+ SAS VERSION : SAS 9.4
+ FIRST DATE : 14 Oct 2019
+ WRITTEN BY : DW Randomization Statistician
+ COMMENTS : Sample Size Calculation & Power for EPO_Biosimilar
+ : Reference: PDA10 Study
*****

proc power;
  twosamplemeans test=equiv_add
  lower = -0.5
  upper = 0.5
  meandiff = 0
  stddev = 0.8
  groupweights = (1 1)
  ntotal = .
  power = 0.9;
run;

```

Figure 4. SAS code used in determining study subject number

Figure 5. SAS output

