6.2 Dosage, Administration, and Administration Period

The drug dose should be individualized, during titration period Eprex® doses should be closely titrated to achieve target Hb range 10-12 g/dl. During maintenance period, the administration dose of Eprex® and Epodion® is equal to the previous dose in titration period. Dose is allowed to be increased or decreased during maintenance period at an appropriate level to maintain Hb level 10-12 g/dl according to condition of subjects. Route of administration for this study is Intravenous injection (IV). Investigational product will be administered when subject enrolled until the end of the study.

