7.4.1 Primary Endpoint

Change in Hb levels from baseline to the evaluation period

Descriptive statistics will be provided by treatment group. The difference between treatment groups will be determined by ANCOVA (analysis of covariance) model with treatment as factor, and baseline Hb level and the change in weekly dosage per kg body weight from baseline to the evaluation period of Epodion® or Eprex® as covariates.

Therapeutic equivalence of Epodion® to the comparator Eprex® will be demonstrated if the two-sided 90% confidence interval of the difference of mean changes in Hb levels between treatment groups lay within the interval of ± 0.5 g/dL.

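### The same 100 subjects are called enrolled in one place and evaluated in another, and the protocol does not say whether they are counted before or after the run-in

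*Protocol*

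**What the plan says.** Protocol section 3.2 (Rationale Number of Subject) sets the target: "A sample size of 90 subjects will be determined with difference 0 g/dL, standard deviation 0.8 g/dL, statistical power 90%, randomization ratio 1:1". The claim to be supported is equivalence, tested at the 5% level against a margin of ±0.5 g/dL. The section then inflates: "After an assumption of 10% drop-out rate for this trial, about 100 subjects will be enrolled to the trial".

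The synopsis table under Number of subjects gives 50, 50 and 100 in a row headed "Evaluated Case". The table in section 3.2.1 also labels 50 per arm as evaluated. The text above that table gives the total of 100, then the filter ("Only subject who achieve baseline target Hb level 10-12 g/dL will continue to maintenance period"), then 1:1 randomisation.

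Titration and a four-week baseline evaluation come before randomisation. Footnote 3 to the synopsis timeline classes a subject who misses the Hb target within eight weeks of titration as a screening failure. Section 5.2 adds further conditions for randomisation, including iron status, dry weight and dose stability. Section 6.2 says of dosing: "Investigational product will be administered when subject enrolled until the end of the study".

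The primary efficacy set is the per-protocol set (protocol 7.1.3, SAP 1.3).

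**The concern.** A 10% drop-out allowance separates the number who enter from the number analysed, so 100 cannot be both. The protocol also never says which entry point it means. Subjects can be lost at three stages: between titration and randomisation, between randomisation and the evaluation period, and through exclusion from the per-protocol set. Only one allowance is given, and it is called drop-out.

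If a site or the sponsor closes recruitment at 100 titration entrants, every run-in failure comes out of the 90. The term also has an operational use, because section 9.10 lets the sponsor withdraw the study at an institution when the enrolment target is missed.

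**Working it through.** **Inputs.** N = 90, SD 0.8 g/dL, true difference 0, margin ±0.5 g/dL, 1:1 allocation and 10% drop-out come from section 3.2. The code there requests an equivalence test ("twosamplemeans test=equiv_add") with no alpha option, so I use the stated 5% for each one-sided test. This agrees with section 7.4.1: "Therapeutic equivalence of Epodion® to the comparator Eprex® will be demonstrated if the two-sided 90% confidence interval of the difference of mean changes" lies within ±0.5 g/dL. The documents give no run-in failure rate f, so every value of f below is an assumption.

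**Step 1: the plan's inflation.** N/(1 − d) = 90/(1 − 0.10) = 100. This reproduces, and it makes 100 the number before the loss and 90 the number after it. Section 3.2 does not call the 90 evaluable; that follows from the inflation.

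**Step 2: the evaluated label.** If 100 must be evaluated, 100/0.9 = 111.1, so about 112 must be randomised. If 100 enter, 90 are evaluated, about 45 per arm. The tables and section 3.2 therefore conflict whatever the run-in failure rate.

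**Step 3: where the 100 is counted.** Counted at titration entry, the number randomised is 100(1 − f) and the number analysed is 90(1 − f). Ending with 90 would take 100/(1 − f) entrants, rounded up. Power is exact for two one-sided t tests: with n per arm, it is the probability that |D| < 0.5 − t(0.95, 2n − 2) × s × √(2/n), averaged over the sampling distribution of s.

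| Assumed f | Randomised | Analysed | Power | Entrants needed for 90 |
|---|---|---|---|---|
| 0 (100 are randomised) | 100 | 90 | 80.5% | 100 |
| 5% | 95 | 85.5 | 77.8% | 106 |
| 10% | 90 | 81 | 74.7% | 112 |
| 20% | 80 | 72 | 67.3% | 125 |
| 30% | 70 | 63 | 58.1% | 143 |

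**Step 4: power with no run-in loss.** A normal approximation checks the first row. SE = 0.8 × √(2/45) = 0.169; 0.5/0.169 = 2.965; power = 2Φ(2.965 − 1.645) − 1 = 2Φ(1.320) − 1 ≈ 0.813. The exact figure is 80.5%. At 100 analysed it is 85.5%. Reaching 90% takes 114 (90.5%), or 114/0.9 = 126.7, about 127 randomised. Ninety does match a single one-sided 5% t test (90.3% power) or an equivalence test at 80% power. The SAS output figure is not in the text available, so I cannot say what it showed.

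The two effects must be kept apart. The fall from 90% to 80.5% is present with no run-in loss at all. Run-in loss could account only for the further fall: 80.5 − 77.8 = 2.7 points at 5%, 80.5 − 74.7 = 5.8 points at 10%, and 80.5 − 67.3 = 13.2 points at 20%.

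**The case against.** The strongest reply is that the 100 plainly means randomised subjects. It is split 50/50 by arm, and arms exist only after randomisation. Section 3.2.1 describes the filter and the allocation directly above the table. Footnote 3 classes titration failures as screening failures, which would not normally count towards a target. On that reading the arithmetic is exact. This largely stands, and it is why the fix adopts that reading. It does not rescue the evaluated label, and footnote 3 covers only the Hb target, not the other section 5.2 conditions.

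A reader might go further and infer that 100 cannot deliver 90. The documents do not support that. The evidence for counting at titration entry is suggestive only. Section 6.2 ties dosing to enrolment, and Eprex dosing starts in titration (4.4.2). Sections 7.1.1 and 7.1.2 define the Safety Set from enrolled subjects and the FAS from randomised ones. None of these defines the term. The Safety Set wording fits randomised subjects too, since footnote 4 of the synopsis timeline records adverse events only in maintenance and evaluation.

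On per-protocol losses, section 5.5 uses drop-out language for exclusion from the per-protocol analysis, so the 10% may already be meant to cover both. That is a fair reading, but section 3.2 does not state it.

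On power, a smaller residual SD from the ANCOVA, about 0.71, would bring 90 analysed to roughly 90%. The documents make no such claim.

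**Conclusion.** The point holds as an inconsistency and a missing definition. The labels enrolled and evaluated cannot both apply to the same 100 alongside a 10% drop-out allowance; this needs no assumption. The stage at which the 100 is counted is undefined, and no allowance is made for losses before randomisation. Whether that causes a shortfall is conditional. There is none if the 100 are randomised and total later loss is 10%. If they are titration entrants and 10% are lost later, 85.5, 81 or 72 remain at assumed failure rates of 5%, 10% or 20%.

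A reader might also put the gap between the stated 90% power and the 80.5% at N = 90 down to run-in failures. That would be wrong. The gap follows from the plan's own SD, margin and test, and is a separate error in the sample-size calculation.

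**What to change.** Amend the protocol wording as follows.

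- In sections 3.2 and 3.2.1, state that the 100 are randomised subjects. State that subjects who fail the Hb target or any section 5.2 criterion before randomisation are screen failures, reported separately and not counted in the 100.
- In the synopsis and section 3.2.1 tables, replace the evaluated label with randomised 50/50, about 45/45 expected in the per-protocol set.
- State that the 10% covers drop-out plus per-protocol exclusions.
- Restate the power for 90 analysed subjects as about 80.5% (two one-sided tests at 5% each, SD 0.8 g/dL, margin ±0.5 g/dL, difference 0) in place of 90%. Whether to enlarge the trial to regain 90% is a separate decision.

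The cost is a wording amendment, possibly more subjects screened to reach 100 randomised, and a less favourable stated power.
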